#### **2.4.5.1 Analyses of adverse events**

##### ***Generalities***

The primary focus of AE reporting will be on TEAEs. Pretreatment and posttreatment AEs will be described separately.

If an AE date/time of onset (occurrence, worsening, or becoming serious) is incomplete, an imputation algorithm will be used to classify the AE as pretreatment, treatment-emergent, or posttreatment. The algorithm for imputing date/time of onset will be conservative and will classify an AE as treatment emergent unless there is definitive information to determine it is pretreatment or posttreatment. Details on classification of AEs with missing or partial onset dates are provided in [Section 2.5.3](#).

Incidence tables will present AEs by SOC, HLG, HLT, and PT, sorted in SOC internationally agreed order and HLG, HLT and PT sorted alphabetically for each treatment group, and the number (n) and percentage (%) of participants experiencing an AE. Multiple occurrences of the same event in the same participant will be counted only once in the tables within a treatment phase. The denominator for computation of percentages is the safety population within each treatment group.

Sorting within tables ensures the same presentation for the set of all AEs within the observation period (pretreatment, treatment-emergent, and posttreatment). For that purpose, the table of all TEAEs presented by primary SOC and PT sorted by the internationally agreed SOC order and decreasing frequency of PTs within SOCs will define the presentation order for all other tables unless otherwise specified. In case of equal frequencies of PTs within a SOC, the alphabetic order will be applied. Sorting will be based on the incidence in the efpeglenatide 6 mg group.

The internationally agreed order of SOCs shown below was described in the Introductory Guide MedDRA Version 19.1, September 2016 International Conference on Harmonisation for SOC:

1. Infections and infestations
2. Neoplasms benign and malignant (including cysts and polyps)
3. Blood and lymphatic system disorders
4. Immune system disorders
5. Endocrine disorders
6. Metabolism and nutrition disorders
7. Psychiatric disorders
8. Nervous system disorders
9. Eye disorders
10. Ear and labyrinth disorders
11. Cardiac disorders
12. Vascular disorders
13. Respiratory, thoracic, and mediastinal disorders
14. Gastrointestinal disorders
15. Hepato-biliary disorders
16. Skin and subcutaneous tissue disorders
17. Musculoskeletal, connective tissue, and bone disorders
18. Renal and urinary disorders
19. Pregnancy, puerperium, and perinatal conditions
20. Reproductive system and breast disorders
21. Congenital and familial/genetic disorders
22. General disorders and administration site conditions
23. Investigations
24. Injury, poisoning, and procedural complications

25. Surgical and medical procedures
26. Social circumstances
27. Product issues

### ***Analysis of all treatment-emergent adverse events***

The following TEAE summaries will be generated for the safety population.

- Overview of TEAEs, summarizing number (%) of participants with any
  - TEAE
  - Serious TEAE
  - TEAE leading to death
  - TEAE leading to permanent treatment discontinuation
  - Treatment-related TEAE
  - TEAEs of special interest (AESI)
  - TEAEs requiring specific monitoring (AERSM)
- All TEAEs by primary SOC, HLGT, HLT, and PT, showing number (%) of participants with at least 1 TEAE sorted by the SOC internationally agreed order. The other levels (HLGT, HLT, PT) will be presented in alphabetical order. This sorting order will be applied to all other tables by SOC, HLGT, HLT, and PT, unless otherwise specified.
- All TEAEs by primary SOC and PT, showing the number (%) of participants with at least 1 TEAE, sorted by the internationally agreed SOC order and by decreasing incidence of PTs within each SOC. This sorting order will be applied to all other tables by SOC and PT, unless otherwise specified.
- All TEAEs related to IMP by primary SOC, HLGT, HLT and PT, showing the number (%) of participants with at least 1 TEAE
- All TEAEs by maximal intensity, presented by primary SOC and PT, showing the number (%) of participants with at least 1 TEAE by intensity (ie, mild, moderate, or severe)
- Summary of common TEAEs (eg, PTs with incidence  $\geq 2\%$  in any treatment group) will also be presented by primary SOC, and PT
- Summaries of common TEAEs (eg, PTs with an incidence  $\geq 2\%$  in any treatment group) will be provided as appropriate by primary SOC and PT and by demographic factors including gender (Male, Female), age group (<50,  $\geq 50$  to <65,  $\geq 65$  to <75,  $\geq 75$  years), and race (Asian, Black or African American, White, Other);

Note: For all efficacy and safety subgroup analyses, race groups “Not reported”, “Unknown”, and participants who report more than one race will be considered “Other”.

- Kaplan-Meier curves will be provided, when appropriate, for the time to first onset of the following PTs: nausea, vomiting, and diarrhea

- The frequency of TEAEs over time will be provided for nausea, vomiting and diarrhea, using weekly time intervals up to 56 weeks, ie, [0-1] week, [1-2] weeks, [2-3] weeks, [3-4] weeks, etc. In each time interval, the numerator in the calculation of percentages will be the number of participants with at least 1 TEAE occurring in this time interval. Two types of analyses will be included: (1) only the first event will be counted for each participant and all recurrent events will not be included, and the denominator for the calculation of percentages will be the number of participants at risk at the beginning of the time interval who did not experience a first event in the preceding intervals; and (2) the recurrent events in subsequent intervals will be counted once for each participant in the numerator of the corresponding interval, and the denominator for the calculation of percentages will be the number of participants at risk at the beginning of the time interval. A histogram of the frequency over time (by weekly intervals) will also be presented as appropriate.
- All TEAEs by BMI subgroup (< 30, ≥ 30 kg/m^2)
- All TEAEs by Anti-Efpeglenatide Antibody Status (Positive, Negative)

***Analysis of all treatment emergent serious adverse event(s)***

All serious TEAEs by primary SOC, HLGT, HLT, and PT, showing the number (%) of participants with at least 1 serious TEAE.

- All serious TEAEs related to IMP, by primary SOC and PT, showing the number (%) of participants with at least 1 serious TEAE

***Analysis of all treatment-emergent adverse event(s) leading to treatment discontinuation***

- All TEAEs leading to treatment discontinuation, by primary SOC, HLGT, HLT, and PT, showing the number (%) of participants

***Analysis of adverse events of special interest and adverse events requiring specific monitoring***

Adverse events of special interest (AESI) and adverse events requiring specific monitoring (AERSM) include AE defined in [Section 2.1.4.1](#) and the criteria of AESI and AERSM are in [Table 2](#).

**Table 2 - Criteria for AESI and AERSM**

| AE Grouping           | Criteria   |
|-----------------------|--|
| AESI           |  |
| Pregnancy             | “Pregnancy” or “Partner pregnancy” checked   |
| Symptomatic Overdose  | “Overdose” checked and symptomatic (AEOVSYP) = “Yes”   |
| Increase in ALT >3ULN | “ALT Increase” checked and Yes to the question “Is the event an AESI?” in eCRF form “Adverse Events” |
| AERSM          |  |
| Severe GI event       | AE severity= “severe” using Gastrointestinal disorders CMQ   |
| Severe hypoglycemia   | Any hypoglycemia event which required assistance (from hypoglycemia page)                            |

| AE Grouping                            | Criteria  |
|--|---|
| Pancreatic event                       | Cases reported in eCRF "Suspected or confirmed Pancreatitis" page or AE Category="Pancreatic Neoplasm"  |
| Selected cardiovascular event          | Cases reported in the following specific eCRF pages: 
 
• 'Suspected or confirmed MI/Unstable Angina'
 
• 'Suspected or confirmed cerebrovascular event',
 
• 'Suspected or confirmed heart failure' led to unplanned hospitalization, led to urgent/unscheduled visit to emergency room or an urgent/unscheduled outpatient heart failure treatment unit, or infusion center, or office/practice visit, not followed by hospitalization, or occurred while patient was hospitalized for another reason
 
• Primary cause of death in eCRF "Death (CV)" as Acute MI, Sudden cardiac death, Heart failure or cardiogenic shock, Stroke, Complication of cardiovascular procedure, Other cardiovascular cause, or Undetermined cause of death
 
 |
| Calcitonin and thyroid C-cell neoplasm | Using Calcitonin increase CMQ
Using Medullary thyroid cancer CMQ   |
| Acute renal failure                    | Using Acute renal failure CMQ   |
| Severe injection site reaction         | Intensity = "Severe" + Using Injection site reaction CMQ.   |
| Severe allergic reaction               | Intensity = "Severe" + CMQs for anaphylactic reaction, angioedema, severe cutaneous adverse reaction, anaphylactic/anaphylactoid shock conditions (under SMQ "Shock"), and hypersensitivity.  |
| Severe immune complex disease          | Intensity = "Severe" using Immune complex disease CMQ   |
| Diabetic retinopathy complications     | Cases reported in eCRF "Diabetic Retinopathy Complementary Form"  |

The number of participants, and the percent of participants who experienced TEAEs of special interest and TEAEs requiring specific monitoring will be presented for each AESI and AERSM specified above by PT and treatment group. PTs will be sorted by decreasing frequency in Efpeglenatide 6 mg group.

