## Adverse events requiring specific monitoring

An AE requiring specific monitoring is a serious or nonserious AE of scientific and medical concern specific to the Sponsor's product or program, for which ongoing monitoring may be appropriate. Such events may require further investigation to characterize and understand them. These events should be reported on the AE page and additional information required on specific eCRF page (where applicable) and will only qualify for expedited reporting when serious (fulfilling SAE criteria).

The AE requiring specific monitoring for this study are:

- Severe GI events
- Severe hypoglycemia (see [Section 8.2.5](#))
- Pancreatic events (including abnormal values of pancreatic enzymes (see Appendix 5 [[Section 10.5.2](#)]) - will be adjudicated by CEC
- Major adverse cardiovascular events (MACE, CV death, MI, or stroke) and other specific CV events (eg, heart failure leading to hospitalization) - will be adjudicated by CEC
- Calcitonin increase  $\geq 5.9$  pmol/L ( $\geq 20$  pg/mL) and thyroid C-cell neoplasm (see Appendix 5 [[Section 10.5.3](#)])
- Acute renal failure (see Appendix 5 [[Section 10.5.1](#)] for definition)
- Diabetic retinopathy complications; a written report from professional eye care provider will be required
- Severe injection site reaction
- Severe allergic reactions
- Severe immune complex disease

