#### **10.5.2.2 Elevation of amylase and/or lipase $>2 \times$ ULN with clinical signs and/or symptoms**

In the presence of clinical signs and/or symptoms evocative of pancreatitis (as previously described) associated with elevated amylase and/or lipase, treatment with the IMP should be promptly and at least temporarily discontinued pending further clinical evaluation and diagnosis confirmation. Clinical signs and/or symptoms are to be documented in the source data. A laboratory determination of amylase and lipase must be obtained at the time of the event and again within 48 hours or earlier as clinically indicated. If the value(s) remain(s)  $>2 \times$  ULN, then amylase and/or lipase levels should be retested as described in Appendix 5 ([Section 10.5.2.1](#)), or more often if clinically indicated.

A gastroenterologic evaluation and imaging (ultrasound and/or CT or MRI with contrast, as appropriate) must be performed as clinically indicated and as per clinical practice and local guidelines. If a diagnosis of pancreatitis is confirmed, IMP should not be restarted and should be permanently discontinued.

In both cases as previously described in Appendix 5 ([Section 10.5.2.1](#) and [Section 10.5.2.2](#)), all laboratory or clinical documentations must be collected. If the retest result confirms lipase and/or amylase values are  $>2 \times \text{ULN}$ , the event must be reported in the eCRF on the specific AE form and the specific complementary forms, using the appropriate verbatim, eg, “increased amylase and/or lipase” in case of isolated enzyme elevation, “suspected pancreatitis” in the presence of clinical signs evocative of pancreatitis if the diagnosis is suspected but cannot be confirmed or excluded, and “pancreatitis” if the diagnosis has been confirmed.

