#### **2.1.4.1 Adverse events variables**

##### ***Adverse event observation period***

- **Pre-treatment AEs** are AEs that developed or worsened or became serious during the pre-treatment period
- **Treatment-emergent AEs (TEAEs)** are AEs that developed or worsened or became serious during the on-treatment period
- **Post-treatment AEs** are AEs that developed or worsened or became serious during the post-treatment period

All AEs (including SAEs, AEs of special interest and AEs requiring specific monitoring) will be coded to a lower-level term (LLT), preferred term (PT), high-level term (HLT), high-level group term (HLGT), and associated primary system organ class (SOC) using the version of MedDRA currently in effect at the time of database lock.

Adverse events of special interest (AESIs) include the following:

- Pregnancy of a female participant entered in a study as well as pregnancy occurring in a female partner of a male participant entered in a study with IMP/NIMP.
- Symptomatic overdose (serious or nonserious) with IMP/NIMP
- Increase in alanine aminotransferase (ALT) >3 x upper limit normal (ULN)

Adverse events requiring specific monitoring include the following terms:

- Severe gastrointestinal (GI) events
- Severe hypoglycemia
- Pancreatic events (including abnormal values of pancreatic enzymes, pancreatitis and pancreatic neoplasm)
- Selected cardiovascular events (CV death, MI, stroke, heart failure leading to hospitalization, unstable angina, and transient ischemic attack (TIA))
- Calcitonin increase ( $\geq 5.9$  pmol/L ( $\geq 20$  pg/mL)) and thyroid C-cell neoplasm
- Acute renal failure
- Diabetic retinopathy complications

- Severe injection site reaction
- Severe allergic reactions
- Severe immune complex disease

Independent Clinical Endpoint Committee(s) [CEC(s)] will review, assess and/or adjudicate all events of death, selected CV events and pancreatic events.

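### SAP Table 2 does not implement the SAP's own definitions of two specifically monitored events: the pancreatic row has no enzyme criterion, and the cardiovascular row adds heart failure without hospital admission

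*SAP*

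**What the plan says.** SAP 2.1.4.1 lists the adverse events requiring specific monitoring (AERSM). The pancreatic entry reads "Pancreatic events (including abnormal values of pancreatic enzymes, pancreatitis and pancreatic neoplasm", so it has three components. Protocol 8.3 has the same enzyme element: "Pancreatic events (including abnormal values of pancreatic enzymes". The cardiovascular entry in SAP 2.1.4.1 is a list without an opening such as 'for example': "Selected cardiovascular events (CV death, MI, stroke, heart failure leading to hospitalization, unstable angina, and transient ischemic attack (TIA".

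SAP 2.4.5.1 then ties the analysis to that list. It says that "Adverse events of special interest (AESI) and adverse events requiring specific monitoring (AERSM) include AE defined in" Section 2.1.4.1, and it sends the reader to Table 2 for the criteria. The pancreatic criterion there is "Cases reported in eCRF 'Suspected or confirmed Pancreatitis' page or AE Category='Pancreatic Neoplasm". The heart-failure criterion covers unplanned hospitalisation and also urgent or unscheduled care at an emergency room, treatment unit, "infusion center, or office/practice visit, not followed by hospitalization, or occurred while patient was hospitalized for another reason".

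Protocol 10.5.2.2 makes any retest-confirmed amylase or lipase value above 2 x ULN reportable on the AE form and on complementary forms that it does not name. It gives a separate reporting term for use "in case of isolated enzyme elevation", distinct from the terms for suspected and for confirmed pancreatitis.

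**The concern.** A definition and its counting rule should select the same events. Here a programmer working from SAP 2.1.4.1 and one working from Table 2 could produce different AERSM counts in two rows, and each could say that the SAP was followed.

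The pancreatic row matters more. Protocol 3.1 names amylase and lipase among the safety parameters of special interest for the GLP-1 RA class, and this trial compares two drugs of that class. If isolated enzyme elevations are left out, the row labelled as pancreatic events reports less than the protocol says it contains. The heart-failure row errs the other way: its label implies admitted cases, but its content is wider.

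**Working it through.** No arithmetic on trial figures applies, because the documents give no event rates for either category. The check sets the texts side by side.

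**Pancreatic row**

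| Component in SAP 2.1.4.1 | Criterion in Table 2 |
|---|---|
| Abnormal enzyme values | None named |
| Pancreatitis | Pancreatitis eCRF page |
| Pancreatic neoplasm | AE category for pancreatic neoplasm |

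1. Protocol 10.5.2.2 uses three reporting terms: raised enzymes alone, suspected pancreatitis, and pancreatitis. The title of the page selected in Table 2 corresponds to the second and third only.
2. An isolated elevation can therefore enter the row only if the site also opened the pancreatitis page. Let E be the number of participants in an arm whose only pancreatic event is a confirmed isolated elevation, and p the share of them with that page completed. The number not counted is E x (1 - p). If p = 1 the loss is 0; if p = 0 it is E. The documents fix neither E nor p.
3. The omission is not the table's general style. The calcitonin row of Table 2 gives the laboratory increase its own criterion, next to the one for the thyroid neoplasm.

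**Do other outputs supply the defined count?**

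- General TEAE tables (SAP 2.4.5.1): enzyme events reported as AEs appear by preferred term and arm, but not grouped with the other pancreatic events.
- Laboratory abnormality table (SAP Appendix B): the cut-off for amylase and lipase is 3 x ULN or higher. Confirmed values above 2 and below 3 x ULN are reportable AEs under protocol 10.5.2.2 but do not reach this table.
- Adjudicated events (SAP 2.4.5.1): pancreas-related events go to the committee, but the summary shows only those positively adjudicated. Nothing says that isolated elevations would be displayed.

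**Heart failure**

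| Situation | SAP 2.1.4.1 | SAP adjudicated-event analysis | SAP Table 2 |
|---|---|---|---|
| Led to hospital admission | Yes | Yes | Yes |
| Urgent visit, no admission | No | No | Yes |
| Arose during a stay for another reason | Not stated | Not stated | Yes |

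This mismatch is on the face of the text and does not depend on any unseen form.

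**Where it shows**

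Table 2 determines the AERSM tables by preferred term, the AERSM line in the TEAE overview and the AERSM listing. SAP 2.4.5 describes the safety analysis as essentially descriptive, with no systematic testing.

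**The case against.** The strongest reply on the pancreatic row is that the pancreatitis page may itself be one of the complementary forms required for every confirmed elevation. Table 2 would then capture isolated elevations and show them by preferred term. The eCRF is not among the documents, so this cannot be ruled out. A reader might infer from the page title that all isolated elevations drop out; the documents do not support that as fact. What remains is that the SAP never says the page serves this purpose. Counting then rests on whether a site opened the page, in a trial where sites know which drug is given, and not on the retest result that makes the event reportable.

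On heart failure, protocol 8.3 gives admitted heart failure only as an example, and SAP Table 1 records that version 2 updated the AERSM definitions in 2.4.5.1. Table 2 may be the intended later definition, with 2.1.4.1 left unaligned. A wider descriptive count also hides nothing. All of this stands as a reason not to call the row wrong. It does not remove the conflict: Table 1 records no decision to widen heart failure or to leave out enzymes, and 2.1.4.1 still carries the narrower text.

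It is also fair that the comparison of arms on enzyme events is not lost. The general TEAE tables show them, and the common-TEAE table would too if the preferred term reaches its 2% example threshold in any arm. Chemistry results are listed and summarised by visit.

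**Conclusion.** The concern holds as an unreconciled conflict between a definition and its counting rule, in two rows. For heart failure the difference is explicit. For pancreatic events the missing criterion is explicit, but its effect is not: the loss lies between none and all of the confirmed isolated elevations.

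A reader might go further and conclude that both counts are wrong, or put a percentage on the pancreatic loss. Neither follows. The documents do not say which text governs, do not show the eCRF and give no rates. Nor do they name heart failure as a class concern; protocol 3.1 names amylase and lipase. No hypothesis, margin or efficacy decision is touched. The point still deserves correction, because the pancreatic grouping is defined in both documents and no other planned output reliably reproduces it.

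**What to change.** - **Pancreatic row of Table 2:** keep the two existing criteria and add 'OR AEs coded to increased amylase and/or lipase (confirmed >2 x ULN)'. Show enzyme elevation, pancreatitis and neoplasm as sub-rows, counting each participant once in the row total. If the pancreatitis page already captures these events, the addition changes nothing.
- **Heart failure:** decide whether cases without admission belong in the AERSM, and make SAP 2.1.4.1 and Table 2 say the same. Show hospitalised and other heart failure on separate rows. The hospitalised row then uses the same event definition as 2.1.4.1 and the adjudicated analysis, although the adjudicated count may still be lower because it keeps only positively adjudicated events.
- **Optional:** add a >2 x ULN row for amylase and lipase to the laboratory abnormality table, so that laboratory and AE counts can be compared.

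The cost is a few lines of SAP text and minor programming, with no new data collection. The displayed pancreatic count may become less favourable.

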***Analysis of adjudicated events***

All events of death, selected cardiovascular events (MI, stroke, unstable angina leading to hospitalization, and heart failure leading to hospitalization), any pancreas related events, and other selected AEs (as defined in the CEC charter) will be reviewed, assessed and adjudicated by CEC.

The number (%) of patients with an event positively adjudicated by CEC will be summarized by treatment group.

### ***Analysis of pretreatment and posttreatment adverse events***

- All pretreatment AEs by primary SOC and PT, showing the number (%) of participants with at least 1 pretreatment AE
- All posttreatment AEs by primary SOC and PT, showing the number (%) of participants with at least 1 posttreatment AE
- All pretreatment SAEs by primary SOC and PT, showing the number (%) of participants with at least 1 pretreatment SAE
- All posttreatment SAEs by primary SOC and PT, showing the number (%) of participants with at least 1 posttreatment SAE

